7.2.2.1 Quantification of the relative CBV for differentiating tumor grade (off-site assessment)

For each DSC-MRI perfusion, the rCBV will be calculated on the generated CBV perfusion map. The regions of interest (ROIs) will be placed by off-site readers on the tumor for providing tumor CBV and also on normal tissue (contralateral normal-appearing white matter) for providing referenced CBV.

| | | |
|---|--|----------------------------|
|  CONFIDENTIAL | Protocol No. GDX-44-016 Version No. 1.0 - ITA Date 15 March 2023 | F015919-05 Page 30 / 59 |
|---|--|----------------------------|

To be sure that the imaged tumor is the same as the tumor biopsied, localization and size of the tumor assessed by the off-site readers will be matched with the standard of truth for grading gliomas. Standard of truth will be histopathological results collected on site (diagnosis based on 2021 WHO classification of CNS tumors).

7.2.2.2 Evaluation of the T2* signal intensity time curve and assessment (on-site and off-site assessment)

T2* signal intensity time curve will be visually assessed by on-site and off-site readers for the reliability of the curve in providing sufficient information for diagnosis purpose. If the curve is assessed as reliable, the full-width at half-maximum (FWHM) and the maximum signal drop will be measured by off-site readers only.

Readers will record their confidence in diagnosis based on the reliability of the curve using a 5-point scale:

- 1 = nil: very uncertain
- 2 = poor: uncertain
- 3 = moderate: moderately certain
- 4 = high: good certainty
- 5 = excellent: very certain

An overview of the imaging evaluation criteria to be assessed by the on-site reader (investigator (INV)) and the Independent Blinded Readers (IBR) is provided in the table below:

Table 2: Allocation of imaging evaluation criteria assessment per type of reader

| Evaluation criteria | Readers |
|--|---------|
| Technical adequacy of CBV map | IBR/INV |
| Diagnostic quality of CBV map | IBR/INV |
| r-CBV quantification | IBR |
| Visual assessment of T2* signal intensity time curve | IBR/INV |
| Maximum signal drop and FWHM T2* signal intensity time curve assessment | IBR |

7.2.3 *Recording of Adverse events*

Adverse events (AE), serious or not, related to IMP or not, that occur from the beginning of patient's participation in the trial (Informed Consent Form signature) will be recorded until the end of the participation (see [section 9.1.2](#)).

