Intra-reader variability: individual readers will perform repeat image evaluations of 10% of cases randomly determined. The cases used for intra-reader variability assessment will be re-introduced randomly and re-read during the course of the reading. To minimize recall bias, intra-reader variability will be assessed after an enough number of cases are reviewed and no sooner than two weeks from the original reviews of these patients. Results of the original reviews for these cases will not be available to the reader. Only the first evaluation of a given image set will be included in the efficacy analysis.

8.4.10 ***Lesion tracking/Matching***

Lesion matching will be performed as an independent off-site procedure. The purpose is to guarantee an unambiguous assignment (matching) of the lesions between histopathology and consensus reads for rCBV quantitative evaluations. It will be carried out by a third IBR in blinded condition based on the consensus read results and histopathological data lesion identification (size, location). Once the concordance process is done, a correspondence/tracking lesion table should be obtained, so that lesions could be compared for the analysis.

8.4.11 ***Image Archive and Final Deliverables***

All imaging data will be maintained in a secure environment. The Imaging Core Laboratory will maintain a centralized image archive that will contain every imaging examination received from the clinical investigators for the trial. Measurements will also be stored so that these data may be audited if necessary. A copy of images transferred by the investigators to Imaging Core Laboratory will be transferred to Guerbet after database lock for archiving.

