The Mann-Whitney U-test will be used to test the difference in rCBV between the two trial arms by tumor grade categorization (low and high grade) and between patients with high-grade and low-grade gliomas, within each of the two study arms at the significant level of 5%. The analysis will be performed for off-site assessment and presented for each off-site reader and overall (taking into account the consensus decision).

If more than one lesion were detected by a reader, the maximum value for rCBV will be considered for the analysis at reader level. For the overall rCBV analysis taking into account the consensus decision, the maximum value for rCBV of consensus reading will be considered. If no consensus was needed, the maximum value for rCBV between the two off-site readers will be considered.

Two analyses will be performed. The first one will consider the gliomas' grade categorization (high-grade versus low-grade) according to the stratification factor used at randomization, the second one will use the tumor grade categorization as per histopathological results (if any) collected during the study.

Categorization as per histopathological results will be the following:

- Grade 1 and Grade 2 = Low grade,
- Grade 3 and Grade 4 = High grade.

The Benjamini-Hochberg method will be used to account for multiple testing for the two analyses separately.

Grade per categorization (high-grade versus low-grade) according to the stratification factor used at randomization will be cross tabulated with the categorization of the grade as per off-site reader assessment, by treatment arm.

If more than one lesion were detected by a reader, the worst grade according to rCBV will be considered. Then, for the overall analysis of grade according to rCBV taking into account the consensus decision, the worst grade according to rCBV of consensus reading will be considered. If no consensus was needed, the worst grade according to rCBV between the two off-site readers will be considered. Moreover, for patients with histopathological results, categorization of the grade per histopathology will be cross tabulated with the categorization of the grade as per off-site reader assessment, by treatment arm.

Categorization as per off-site reader assessment will be the following (according to the Imaging Charter V1.0):

- $rCBV < 1.75$ = Low grade,
- $rCBV \geq 1.75$ = High grade.

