Table 14.2.2.16 rCBV by treatment arm assigned at randomization and by grade (stratification variable at randomization) – Comparison within arms – Off-site PPS

Table 14.2.2.17 rCBV by treatment arm assigned at randomization and by grade (stratification variable at randomization) – Comparison between arms – Off-site FAS

Table 14.2.2.18 rCBV by treatment arm assigned at randomization and by grade (stratification variable at randomization) – Comparison within arms – Off-site FAS

Table 14.2.2.19 rCBV by treatment arm assigned at randomization and by grade (according to histopathology) – Comparison between arms – Off-site PPS - Patients With a Detected Lesion Matching Histopathology

Table 14.2.2.20 rCBV by treatment arm assigned at randomization and by grade (according to histopathology) – Comparison within arms – Off-site PPS - Patients With a Detected Lesion Matching Histopathology

Table 14.2.2.21 rCBV by treatment arm assigned at randomization and by grade (according to histopathology) – Comparison between arms – Off-site FAS - Patients With a Detected Lesion Matching Histopathology

Table 14.2.2.22 rCBV by treatment arm assigned at randomization and by grade (according to histopathology) – Comparison within arms – Off-site FAS - Patients With a Detected Lesion Matching Histopathology

Table 14.2.2.23 Grade assessed by off-site readers (based on rCBV) by treatment arm assigned at randomization and by grade (stratification variable at randomization) – Off-site PPS

Table 14.2.2.24 Grade assessed by off-site readers (based on rCBV) by treatment arm assigned at randomization and by grade (stratification variable at randomization) – Off-site FAS

CONFIDENTIAL	STATISTICAL ANALYSIS PLAN N° GDX-44-016 VERSION N° 4.0 (REF I011622)	F015830-03 Page 32 / 35
--------------	--	----------------------------

Table 14.2.2.25 Grade assessed by off-site readers (based on rCBV) by treatment arm assigned at randomization and by grade (according to histopathology) – Off-site PPS - Patients With a Detected Lesion Matching Histopathology

Table 14.2.2.26 Grade assessed by off-site readers (based on rCBV) by treatment arm assigned at randomization and by grade (according to histopathology) – Off-site FAS - Patients With a Detected Lesion Matching Histopathology

Table 14.2.2.27 Reliability of the T2* signal intensity time curve for diagnosis and level of diagnosis confidence by treatment arm assigned at randomization at Lesion Level – Off-site PPS

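### In patients with more than one detected lesion, the histopathology-based rCBV analyses take the maximum rCBV or worst grade over all lesions, not the value of the lesion matched to the biopsy

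*SAP*

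**What the plan says.** **Protocol.** Section 7.2.2.1 makes histopathology the standard of truth for glioma grade and has the location and size of the tumour read off-site matched to it. The stated reason is "To be sure that the imaged tumor is the same as the tumor biopsied". Section 8.4.10 gives the task to a third blinded reader, who is to "guarantee an unambiguous assignment (matching) of the lesions between histopathology and consensus reads for rCBV quantitative evaluations". The product is a lesion tracking table intended for the analysis.

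**SAP, choice of value.** Section 2.2.2 has rCBV assessed per lesion but analysed per patient, or per patient and reader. Section 5.5.3 then says how several lesions become one value:

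- For each reader: "If more than one lesion were detected by a reader, the maximum value for rCBV will be considered for the analysis at reader level".
- Overall, after a consensus read: "the maximum value for rCBV of consensus reading will be considered".
- Overall, with no consensus needed: "the maximum value for rCBV between the two off-site readers will be considered".

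Only after these rules does it introduce the two analyses. The first uses the randomisation stratum; for the other, "the second one will use the tumor grade categorization as per histopathological results (if any) collected during the study". For the rCBV-based grade (cut-off 1.75) the rule is "If more than one lesion were detected by a reader, the worst grade according to rCBV will be considered". The same paragraph goes on to cross-tabulate reader grade against histological grade.

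**SAP, use of the match.** Section 2.2.2 describes matching as a check that one of the tumours read corresponds to the reference tumour. In the table list, the histopathology tables (14.2.2.19-22 and 14.2.2.25-26) carry the restriction "Patients With a Detected Lesion Matching Histopathology".

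**The concern.** Comparing the two agents in differentiating glioma grade through rCBV is a secondary objective. A histological grade belongs to the lesion that was sampled. The maximum over a patient's lesions is a patient-level summary, and the lesion that supplies it need not be the sampled one.

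Take a hypothetical patient with two lesions. The biopsied lesion is grade 2 with rCBV 1.2, and an unsampled lesion has rCBV 2.6. As written, the plan enters 2.6 in the Mann-Whitney analysis and records high rCBV grade against low histological grade, although the sampled lesion (1.2, below 1.75) agreed with its histology. The reverse can also happen: a biopsied high-grade lesion with a low rCBV is recorded as agreeing because another lesion has a high one.

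At stake is whether the histopathology tables measure agreement between a lesion's rCBV and that same lesion's grade, which is what the protocol set up the matching to secure.

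**Working it through.** **Step 1: does any text restrict the value to the matched lesion?** The maximum rule precedes both analyses and has no exception. The worst-grade rule precedes the histopathology cross-tabulation and has none either. The only place where matching enters the outputs is the table-title restriction, and that names patients. A programmer following the text would keep the patients with a matching lesion and then take the maximum over all their lesions. The protocol asks for a lesion-to-lesion link, and the SAP carries it through only as a patient filter.

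**Step 2: who is affected?** With one detected lesion, the filter ensures that this lesion is the matched one, so the maximum is its own value. Only patients with histology and more than one detected lesion remain. The documents do not give their number.

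**Step 3: direction in the cross-tabulation.** The maximum over a set that contains the matched lesion is never below the matched lesion's value. So the rule can move a patient from low to high rCBV grade and never the other way. This needs no assumption.

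**Step 4: possible size (illustration only).** The plan states no figure to reproduce here. Assumed inputs, none of them in the documents:

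- A histologically low-grade matched lesion reads at or above 1.75 with probability q = 0.20 (80% read below).
- A second lesion has the same distribution, with normal correlation 0, 0.5 or 0.8 to the first.
- A share m = 10%, 20% or 30% of low-grade patients have two lesions.

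In a two-lesion patient with independent lesions, P(called high) = 1 - (1 - 0.20)² = 1 - 0.64 = 0.36. With correlated lesions the bivariate normal gives 0.313 (correlation 0.5) and 0.271 (correlation 0.8). Over all low-grade patients the rate is q + m × (P - q):

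| Correlation | P(called high), two lesions | m = 10% | m = 20% | m = 30% |
|---|---|---|---|---|
| 0 | 0.360 | 0.216 | 0.232 | 0.248 |
| 0.5 | 0.313 | 0.211 | 0.223 | 0.234 |
| 0.8 | 0.271 | 0.207 | 0.214 | 0.221 |

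Using the matched lesion returns every cell to 0.200. The excess runs from 0.7 points (0.10 × 0.071) to 4.8 points (0.30 × 0.16).

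**Step 5: the Mann-Whitney contrast of high against low grade.** Take the same two-lesion model and add an assumed shift of 1 to 2 SD for high-grade lesions. The quantity computed is the probability that a high-grade patient's value exceeds a low-grade patient's. With equal two-lesion shares in both grades it is unchanged or rises slightly, for example from 0.856 to 0.860 at a shift of 1.5 SD, 30% and correlation 0. With unequal shares it moves either way. At a shift of 1 SD and correlation 0 it goes from 0.760 to 0.736 if 30% of low-grade and 10% of high-grade patients have two lesions, and to 0.787 with the shares reversed. The documents do not say which grade has more multi-lesion patients, so the direction is unknown.

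**The case against.** **The table titles imply the matched lesion.** They limit the patients and do not say which lesion supplies the value, while the body of the SAP does say: the maximum. The titles do show that the match is used. A reader might infer that the matching effort is lost, but the filter removes patients whose read lesions do not correspond to the biopsy, and it fully settles single-lesion patients.

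**Multiple lesions may be rare.** They may be. The protocol wording is mostly singular and on-site reading considers one lesion. Yet SAP 1.2 lists the number of lesions detected among the grounds for a consensus meeting, and 5.5.3 writes explicit rules for several lesions, so the case was foreseen.

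**The Imaging Charter may hold a matched-lesion rule.** SAP 1.2 cites the Charter for matching, and it is not available here. Such a rule would still conflict with the explicit SAP rule and would need to be stated there.

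**Matching is defined at consensus level.** This stands in part. Protocol 8.4.10 ties matching to the consensus reads, while SAP 1.2 and 2.2.2 speak of lesions assessed by the off-site readers. A link for each reader's own lesion is not assured, and the fix has to allow for that.

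**The analyses are minor.** They are supplementary, depend on biopsy or surgery within 30 days of the MRI, and individual rCBV values and histopathology will be listed. That limits the weight of the point but does not make the rule fit its purpose.

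**Conclusion.** The point holds as a mismatch between the SAP's rule and the protocol's stated purpose, confined to the histopathology-based rCBV analyses in patients with more than one detected lesion. The maximum and worst-grade rules are reasonable against the randomisation stratum, which is a patient-level grade.

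What is certain is the direction in the cross-tabulation, from low to high rCBV grade only. The illustrative 1 to 5 points rest wholly on the assumptions in the working, and the upper end needs 30% two-lesion patients with uncorrelated lesions.

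Three stronger readings are tempting and not supported:

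- That the rule weakens the low/high contrast: the Mann-Whitney comparison can move either way.
- That it favours one agent: the rule is the same in both arms, randomisation is stratified by grade, and nothing in the documents points to lesion counts that differ by arm.
- That it biases reported sensitivity or specificity: the SAP plans a cross-tabulation and does not prespecify either statistic.

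**What to change.** In SAP 5.5.3, for Tables 14.2.2.19-22 and 14.2.2.25-26:

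- **Overall (consensus) analysis:** use the rCBV and rCBV-based grade of the lesion matched to histopathology in the tracking table.
- **Reader-level analysis:** use the same lesion for each reader where that reader's lesion can be linked to the matched one.
- **No consensus needed:** state how the two readers' values for that same lesion are combined.
- **Reporting:** give the number of multi-lesion patients by arm.

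Keep the maximum and worst-grade rules for the stratum-based analyses. They may be repeated as a sensitivity analysis in the histopathology tables.

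The cost is a short SAP change and some extra programming. Per-lesion rCBV and the tracking table are already planned. A few reader-level values may be missing where a reader's lesion cannot be linked, and these should be counted and reported.

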8.4 Off-Site Reading of Images

Off-site image evaluations are image evaluations performed at sites that have not otherwise been involved in the conduct of the trial and by readers who have not had contact with patients, investigators, or other individuals involved in the trial.

Images will be evaluated by prospective evaluation of the blinded images in a centralized manner. All images will be sent to an imaging core laboratory (ICL), which will prepare the images for evaluation. The file headers of all the images transmitted in DICOM format are to be edited to remove patient or site identification. For all images, any sequence information will be removed. Scalar information in the MR images will be preserved. A complete audit trail of any changes to the file headers will be maintained.

| | | |
|--|--|----------------------------|
|  CONFIDENTIAL | Protocol No. GDX-44-016 Version No. 1.0 - ITA Date 15 March 2023 | F015919-05 Page 34 / 59 |
|--|--|----------------------------|

The blinded image evaluations will be performed by 2 independent blinded readers experienced in brain tumor and perfusion imaging. In case of discordance, a consensus meeting will be organised in order to reach an agreement. The following criterion will be concerned by the consensus in case of discordance:

- The localization of the lesion
- The diagnostic quality of the CBV map (primary criterion).
- rCBV quantification (consensus in the glioma grade, not in the rCBV value)
- Visual evaluation of the T2* signal intensity time curve, including the confidence in the diagnosis.

An imaging eCRF will be used to ensure that the images and the diagnostic findings are properly aligned and to ensure that all data necessary for the trial purpose are documented by the independent blinded readers.

8.4.1 *Manuals and Supplies*

Guerbet (or the ICL) will document the imaging tasks and obligations of the investigational site in an Imaging Manual. As defined in [section 8.2](#), the standardized image acquisition guidelines or imaging protocol will be provided to the sites as part of the Imaging Manual.

In addition, the Imaging Manual will detail the steps required for masking confidential patient information and transferring images to the ICL (if applicable).

Guerbet (or the ICL) will document the central imaging process in a Blinded Imaging Evaluation Charter.

8.4.2 *Site Qualification*

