Assessment and evaluation of the T2* signal intensity time curve at lesion level (on-site and off-site assessment)

T2* signal intensity time curve will be visually assessed by on-site and off-site readers for the reliability of the curve in providing sufficient information for diagnosis purpose.

For on-site assessment, the number and percentage of lesions for whom the reliability of the curve provides suffice information will be tabulated by trial arms.

For the off-site assessment, the number and percentage of lesions for whom the reliability of the curve provides suffice information will be tabulated by trial arms.

CONFIDENTIAL	STATISTICAL ANALYSIS PLAN N° GDX-44-016 VERSION N° 4.0 (REF I011622)	F015830-03 Page 26 / 35
--------------	--	----------------------------

For lesions for whom the reliability of the curve provides suffice information, confidence in diagnosis will be presented, for each arm, by on-site readers and for the off-site assessment for each off-site reader, using a 5-point scale:

- 1 = nil: very uncertain,
- 2 = poor: uncertain,
- 3 = moderate: moderately certain,
- 4 = high: good certainty,
- 5 = excellent: very certain.

Confidence in diagnosis will be summarized qualitatively and quantitatively by trial arm. The on-site and off-site read outcomes will be separately analyzed.

For the overall reliability of the T2* signal intensity time curve taking into account the consensus decision, the worst confidence in diagnosis between the two readers will be considered if no consensus decision was needed (worst case scenario).

Assessment and evaluation of the T2* signal intensity time curve (off-site assessment)

Only for off-site readers, FWHM and the maximum signal drop will be tabulated at lesion level by off-site reader and compared between the trial arms using a Mann-Whitney U-test.

For the overall FWHM taking into account the consensus decision, the mean of values between the two readers for each lesion will be considered if no consensus decision was needed.

For the overall maximum signal drop taking into account the consensus decision, the maximum of values between the two readers for each lesion will be considered if no consensus decision was needed.

If the curve is not reliable, no calculation of FWHM and the maximum signal drop will be performed.

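### Overall rCBV and maximum signal drop take the higher of the two readers' values, which adds an upward bias that grows with reader scatter and can differ between arms

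*SAP*

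**What the plan says.** SAP 5.5.3 forms an overall off-site value for three continuous measures. Where the readers did not need a consensus, the rules are:

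- rCBV: "If no consensus was needed, the maximum value for rCBV between the two off-site readers will be considered".
- Maximum signal drop: "the maximum of values between the two readers for each lesion will be considered if no consensus decision was needed".
- FWHM: "the mean of values between the two readers for each lesion will be considered if no consensus decision was needed".

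For rCBV cases that went to consensus, "the maximum value for rCBV of consensus reading will be considered". Protocol 8.4 limits what that consensus settles: "rCBV quantification (consensus in the glioma grade, not in the rCBV value". SAP 1.2 says the same.

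The overall values are then tested. For rCBV, "The Mann-Whitney U-test will be used to test the difference in rCBV between the two trial arms by tumor grade categorization", at 5%. FWHM and maximum signal drop are "compared between the trial arms using a Mann-Whitney U-test". rCBV is also analysed for each reader, and FWHM and signal drop are tabulated by reader. The protocol contains no rule that takes the maximum between readers.

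**The concern.** Taking the highest lesion in a patient chooses between different tumours. Taking the higher reader chooses between two measurements of the same tumour, and the choice is made partly by measurement error. The result sits above the true value by an amount that depends on how far the readers scatter.

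The arms use different agents at different gadolinium doses, and the trial asks whether map quality differs between them. Reader scatter in ROI placement and curve measurement could therefore differ by arm. If it does, the noisier arm is pushed upward, and a Mann-Whitney test can report a difference that is only scatter, or can mask a real loss of signal.

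Nothing else in the plan would correct this. A large disagreement in rCBV value on the same side of the 1.75 cut-off does not trigger the grade consensus. Kappa is planned only for the primary criterion. Sensitivity analyses are listed as not applicable. The Benjamini-Hochberg adjustment of the rCBV p-values cannot repair a biased input.

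**Working it through.** **Inputs from the documents.** The combination rules, the tests and the 5% level are in SAP 5.5.3. The 62 per arm is in SAP 3.3. It reproduces: (1.96 + 0.842)² × 2 × 0.94 × 0.06 / 0.12² = 61.5, so 62 per arm, and 124 / 0.9 = 137.8, so 138 in total. This is the only design calculation in the documents; there is none for rCBV or signal drop.

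**Inputs assumed.** The documents give no reader SD, no between-patient SD and no split by grade. I assume reader SDs of 10% to 30% of the true value, between-patient log-SDs of 0.3 and 0.5, errors independent between readers, and an even grade split, so 62 / 2 = 31 per arm in each stratum. Signal drop is taken as one lesion per patient, 62 per arm.

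**Bias and precision.** For two independent normal readings with error SD s:

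- Expected maximum = true value + s/√π = true value + 0.564s. At s = 10%, 20% and 30% the overstatement is 5.6%, 11.3% and 16.9%.
- The mean of the two readings has no such bias.
- Error variance of the maximum = (1 − 1/π)s² = 0.68s². For the mean it is 0.50s².
- Spurious arm difference = 0.564 × (difference in reader SD). For 20% vs 30% this is 5.6 percentage points; for 10% vs 30% it is 11.3.

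**False-positive rate.** I simulated the two-sided 5% Mann-Whitney test with identical true distributions in both arms. The ranges cover both between-patient SDs and two error models (error added on the log scale, and error proportional to the true value). No case goes to consensus here.

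| Overall value = higher reader | Equal scatter | 10% vs 15% | 20% vs 30% | 10% vs 30% |
|---|---|---|---|---|
| rCBV within grade, 31 per arm | about 5% | 5–7% | 5.5–8% | 8–22% |
| Signal drop, 62 per arm | about 5% | 5–8% | 7–12% | 13–40% |

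With the mean of the two readers the rate is about 5% in every cell (4.3% to 6.1% across all runs).

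**Allowing for consensus on grade.** In a lognormal rCBV model (between-patient log-SD 0.5, reader log-SD 0.15 vs 0.30), readers on opposite sides of 1.75 go to consensus. With 62 per arm the rate is about 13.5% if the consensus value is again the maximum, and 7.1% to 9.5% if it is the geometric mean. With 31 per arm the corresponding figures are about 9% and 6% to 7%. Consensus dilutes the effect but does not remove it.

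**The case against.** The strongest reply is that a bias between arms needs unequal reader scatter, and the documents offer no evidence of it. That stands: with equal scatter the test is valid, and with modest differences such as 10% vs 15% the inflation is small.

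Four further points carry weight.

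- The rCBV test is run within grade, so rates computed on 62 per arm overstate the problem for that measure. The histology-based analysis is smaller still.
- The rule applies only where no consensus was needed. Consensus is also called for disagreement on the number or location of lesions and on the T2* curve, including confidence. The remaining cases are plausibly those with less scatter.
- The per-reader rCBV analyses and per-reader signal-drop tables carry no between-reader maximum, and individual values are listed by reader. An artefact could be seen and recomputed.
- The rule resembles the SAP's choice of the worst grade between readers, and the Imaging Charter, which is not among the documents, may give a reason. It cannot be said that no rationale exists.

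These points limit the size. They do not justify making the overall result depend on reader scatter. Nor does grading need the maximum: if both readers put a lesion on the same side of 1.75, so does their mean.

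A reader might infer that the rule favours Elucirem, or that the secondary comparisons carry a false-positive rate near 40%. The documents support neither. They do not say which arm would be noisier, and the 40% figure needs a threefold difference in scatter, the unstratified signal-drop comparison and no consensus cases.

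**Conclusion.** The point holds for the overall rCBV and overall maximum signal drop analyses. The upward bias and the loss of precision follow directly from the rule, given reader errors that are at least partly independent. A distorted comparison between arms is conditional on unequal reader scatter, and its size is unknown. It ranges from negligible to about 22% false positives for rCBV and about 40% for signal drop at the extreme of the assumed range, before any dilution by consensus.

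These are secondary comparisons, and the primary non-inferiority conclusion does not depend on them. The change is worth making because it costs little and the SAP already uses the better rule for FWHM.

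**What to change.** In SAP 5.5.3, for cases where no consensus was needed:

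- Define overall maximum signal drop as the mean of the two readers for each lesion, as for FWHM.
- Define overall rCBV by averaging the two readers for each lesion first, then taking the highest lesion mean in the patient. Averaging each reader's own highest lesion would not do, because in a patient with several lesions the two may be different tumours. Matching is feasible, since disagreement on the number or location of lesions already goes to consensus.
- Keep the between-reader maximum as a sensitivity analysis.

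The separate rule for overall grade can stay as it is. It would help to state in the same place how the rCBV value is set after a consensus that settles only the grade, and to report inter-reader agreement on both measures by arm.

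The core change costs two sentences and minor programming. Reported rCBV and signal-drop values become slightly lower.
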